### 3.3.3. Risk Factors for CINV

At the time of the collection of demographic and medical history data at the screening visit (Visit 0, see details below), all the predictive individual factors will be collected and the patients' risk score automatically calculated. These parameters will be used to identify the patients with a CINV risk score  $\geq 13$  (see 3.3.1., Inclusion Criteria). If the patients comply with all the inclusion and exclusion criteria, they are enrolled into the study. The parameters from 1 to 7 will be used to identify the patients at high risk of CINV:

1. Nausea and/or vomiting in the prior cycle of chemotherapy
2. Use of non-prescribed antiemetics at home in the prior cycle of chemotherapy
3. Platinum or anthracycline-based chemotherapy
4. Age  $< 60$  years
5. Expectation for (anticipating) nausea and/or vomiting
6. History of morning sickness during previous pregnancy
7. Cycle of chemotherapy
8.  $< 7$  h of sleep the night before chemotherapy (to be obtained at day of chemotherapy)
9. History of any nausea and vomiting such as motion sickness, vestibular dysfunction...
10. Anticipatory nausea and/or vomiting
11. Anxiety over the past 24hrs (to be obtained at day of chemotherapy)
12. Alcohol intake (number of units per week)
13. Gender
14. Fatigue experience (symptom)
15. Smoking status
16. Weight

Parameters from 8 to 16 are defined as additional risk factors and will not influence the risk score.

The risk factors for CINV are checked at each cycle before chemotherapy and are used for patient's risk score re-calculation. This result of the re-calculation has no impact on patient's participation in the study and the randomized group.

The percent of patients using carboplatin will be limited to 20% of the planned number of patients in the study: the maximum number of patients using carboplatin in this study will be 106.

CONFIDENTIAL

Confidential	MyRisk	Date: 05 February 2024
	Protocol	
	PROTOCOL NUMBER: IBA1160	Version: 5.1

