7.1. Study Database and External Data

Data collected and validated in the clinical study database will be analyzed. Data from the Patient's diary, MAT and FLIE questionnaires will be digitalized to become a part of the clinical database. No other external data are planned to be used for the analysis.

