9.8. Secondary Analysis

An analysis with development of CINV as a dependent variable will be performed to identify additional potential risk factors of CINV. The analysis will be performed using the Per Protocol population. Data on 16 risk factors will be collected before each chemotherapy cycle:

1. Nausea and/or vomiting in the prior cycle of chemotherapy
2. Use of non-prescribed antiemetics at home in the prior cycle of chemotherapy
3. Platinum or anthracycline-based chemotherapy
4. Age < 60 years
5. Expectation for (anticipating) nausea and/or vomiting
6. History of morning sickness during previous pregnancy
7. Cycle of chemotherapy
8. <7 h of sleep the night before chemotherapy (to be obtained at day of chemotherapy)
9. History of any nausea and vomiting such as motion sickness, vestibular dysfunction...
10. Anticipatory nausea and/or vomiting
11. Anxiety over the past 24hrs (to be obtained at day of chemotherapy)
12. Alcohol intake (number of units per week)
13. Gender
14. Fatigue experience (symptom)
15. Smoking status
16. Weight

The first 7 factors are used throughout this study to identify patients with high risk of CINV. The CINV score is recalculated for each of patient's cycles and has no impact on patient's participation in the study and the randomized group.

The purpose of secondary analysis is to identify other, potentially predictive factors among the 9 additional ones.

A simple logistic regression model with the development of CINV over three cycles of chemotherapy will be conducted to identify a set of factors with the largest potential contribution to CINV and those with P-value ≤ 0.25 will be taken

into further consideration. Generalized estimating equations (GEE), which adjust for patient clustering by chemotherapy cycle, will be used to determine the final set of additional risk factors.

By using reclassification analysis NRI (Net Reclassification Improvement) we will redistribute the patients according to the new set of risk factors. Finally, the set of primary risk factors and the new set of risk factors will be compared, by presenting NRI_e and NRI_{ne} , the event- and non-event reclassification index.

These indices can be interpreted as a change in True Positive Rate and the negative of change of False Positive Rate, when using a new model and comparing it to the previously used one.

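### The NRI in SAP 9.8 is biased upward because factors are selected and scored in the same patients without internal validation, and its reference model and cut-off are not stated

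*SAP*

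**What the plan says.** SAP 9.8 sets out one sequence in one data set: "The analysis will be performed using the Per Protocol population". Its aim is given as "The purpose of secondary analysis is to identify other, potentially predictive factors among the 9 additional ones". The steps are:

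- Simple logistic regression as a screen: "those with P-value ≤ 0.25 will be taken" forward.
- GEE, which "will be used to determine the final set of additional risk factors". No retention criterion is given.
- NRI: "By using reclassification analysis NRI (Net Reclassification Improvement) we will redistribute the patients according to the new set of risk factors". The event and non-event parts are reported, and the SAP explains them thus: "These indices can be interpreted as a change in True Positive Rate", with the non-event part as minus the change in false positive rate, relative to the model used before.

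The true/false positive wording implies a two-class rule, but 9.8 gives no cut-off for either model. It describes no split sample, cross-validation, bootstrap or optimism correction. On outside data, SAP 7.1 says: "No other external data are planned to be used for the analysis".

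The only risk cut-off in the documents is a score of at least 13. It is an entry criterion (Protocol 3.3.1 and 3.6.3.2). Protocol 3.3.3 says of the collected factors: "These parameters will be used to identify the patients with a CINV risk score" at or above that value. The score is recalculated before later cycles with no effect on participation.

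**The concern.** An index computed in the data that chose and fitted the factors rewards chance associations as well as real ones. With nine candidates, a lenient screen and no stated final criterion, part of any reported gain will be optimism, and the plan has no step to measure or remove it.

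There is also a question of what the index is compared with. If the comparator is the entry rule, every patient is classed as high risk at cycle 1. The old rule then has no room to gain sensitivity or lose specificity, and an index pooled over cycles mixes this situation with cycles 2-3, where the rule does separate patients.

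Protocol 3.6.1 says the extra factors will be used to refine the predictive model at the end of the trial, so an optimistic or ambiguous NRI would feed into a revised tool.

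**Working it through.** **Step 1. Size of the data set.** The documents state no NRI figure, so the figure to reproduce is the sample size in SAP 9.2: 410 randomised 1:1, 71% v 60%, two-sided 0.05, 80% power, correlation 0.5, missing 0%, 7.5% and 15%. With d = 1, 0.925, 0.85:

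D = [Σd + ρ Σ(j≠k) d_j d_k] / (Σd)² = [2.775 + 0.5 × 5.1225] / 2.775² = 5.336 / 7.701 = 0.693

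n per arm = (1.960 + 0.842)² × [1/(0.71 × 0.29) + 1/(0.60 × 0.40)] × D / (ln OR)² = 7.849 × 9.023 × 0.693 / 0.4899² = 204.5

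The total is 409, or 410 with equal arms, where power is 80.1%. Completers: 410 × 0.85 = 348.5, hence the stated 348. I use 348 as an upper figure for the Per Protocol set, which also requires full compliance.

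**Step 2. The screen.** For nine independent null factors the expected number passing is 9 × 0.25 = 2.25, and P(at least one) = 1 − 0.75⁹ = 92.5%. In simulation, with the simple logistic model fitted to pooled patient-cycles, 3.05 passed on average and at least one passed in 98% of trials, because that step ignores clustering.

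**Step 3. Optimism.** 2,000 trials were simulated, each of 348 patients × 3 cycles with nine null factors. NRI was scored in the same data and in 40,000 new patients. The following are assumptions, not in the documents: CINV taken as no complete response, at (29% + 40%)/2 = 34.5%; entry scores 13, 14, 15 in 45%, 40%, 15%; factor prevalences; no non-prescribed antiemetics; a refitted seven-factor reference; a two-category cut at the event rate; and, where shown, GEE retention at P < 0.05.

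| Final set | Trials averaged | Two-category: same / new / difference | Category-free: same / new / difference |
|---|---|---|---|
| All passing the screen | All | +0.008 / −0.008 / 0.016 | +0.152 / −0.015 / 0.167 |
| GEE P < 0.05 | All | +0.003 / −0.003 / 0.006 | +0.062 / −0.002 / 0.064 |
| GEE P < 0.05 | Factor kept (38%) | +0.007 / −0.008 / 0.015 | +0.163 / −0.006 / 0.168 |

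Further runs under other assumed inputs kept a noise factor in 36% to 40% of trials. When one was kept, two-category NRI ran from +0.007 v −0.008 to +0.011 v −0.010 (difference 0.015 to 0.021), and category-free NRI was +0.18 v −0.01 (0.19).

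**Step 4. Cycle 1 with score ≥ 13 as the old rule.** NRI_e = TPR(new) − TPR(old) and NRI_ne = FPR(old) − FPR(new). Everyone randomised as planned scores at least 13, so TPR(old) = FPR(old) = 1. Hence NRI_e = TPR(new) − 1 ≤ 0 and NRI_ne = 1 − FPR(new) ≥ 0. If the new score only adds points and keeps the cut at 13, both are exactly 0. In the 2,000 trials the largest cycle 1 NRI_e was −0.096. Cycle 1 is 1/3 = 33% of patient-cycles in completers, and 1/2.775 = 36% under the planned missingness.

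**Step 5. Where the bound stops.** From the score table in SAP 7.9, a chemotherapy-naïve patient enters with 13 to 15. With the other factors stable:

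| Prior cycle | Cycle 2 | Cycle 3 |
|---|---|---|
| No nausea/vomiting, no non-prescribed antiemetic | 8 to 10 | 7 to 9 |
| Nausea/vomiting only (+5) | 13 to 15 | 12 to 14 |

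So the old rule does separate patients in cycles 2-3, and simulated NRI_e there was positive in every run. With a refitted reference and an event-rate cut, cycle 1 NRI_e was positive in 7% of all null trials (P < 0.05 retention) to 19% (all passing the screen kept). In the further runs it was positive in 37% to 40% of trials that kept a factor.

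**Step 6. Pooled index against the ≥ 13 rule.** With null factors and P < 0.05 retention, the pooled parts averaged −0.063 (event) and +0.156 (non-event), a total of +0.093. A separate run of 1,000 trials gave +0.10 in the same data and still +0.09 in new patients. That apparent gain comes from refitting and a changed cut-off, not from the added factors, and optimism correction alone would not remove it.

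**The case against.** The strongest defence is one of scope and size. This is a secondary analysis meant to find potentially predictive factors. It touches neither treatment nor eligibility, and lack of optimism correction contradicts nothing in the documents. Nine null factors is a worst case: short sleep belongs to the published tool (Protocol 3.6.1), and the Protocol Introduction cites evidence for several of the others. The P < 0.05 retention and the event-rate cut are assumptions, and with a two-category index the inflation is small. In one set of runs the same-data NRI was not even positive in 27% of the trials that kept a factor.

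All of that stands as a limit on size and priority. It does not remove the bias: real effects would still be measured with optimism when selection and scoring share the same patients. SAP 9.8 points to an external macro for the NRI, but a macro applied at that last step would not repeat the selection.

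A reader might go further and infer that NRI_e can never be positive at cycle 1. The documents do not support this, because 9.8 does not say that the entry rule is the NRI comparator. A reader might also infer that the true-positive-rate reading breaks down at cycle 1. It does not: NRI_e equals TPR(new) − 1 exactly. The restricted range correctly describes patients selected by the rule. It makes the event part look worse, not better, and since the two parts are reported separately, the loss would be visible beside the non-event gain.

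**Conclusion.** The point holds in two parts.

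First, without qualification as to direction: followed as written, SAP 9.8 gives upwardly biased NRI_e and NRI_ne. Under the assumptions in the working, a noise factor is kept in about 37% of trials. Total optimism is then about 0.02 (two-category) or 0.18 (category-free), and about 0.006 or 0.06 averaged over all trials. The SAP's own description of the indices points to the two-category form, so the smaller figures are the likelier ones.

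Second, conditionally: if the old model is score ≥ 13, then at cycle 1 NRI_e ≤ 0 and NRI_ne ≥ 0 whatever the new factors add. This assumes the Per Protocol set holds no patient below 13, which could happen only if that unmet criterion were judged minor. It applies neither to a refitted reference with another cut-off nor to cycles 2-3.

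This is a worthwhile improvement to a secondary analysis, not a threat to the trial. The primary comparison is not affected.

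**What to change.** Amend SAP 9.8 before database lock. The Study Summary of the Protocol leaves the detail of these methods to the SAP.

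- Name the reference model, the cut-off for both models and the GEE retention rule. This comes first: without it even a corrected NRI is undefined.
- Bootstrap by patient the full sequence (screen, GEE, NRI), and report optimism-corrected NRI_e and NRI_ne with intervals.
- Report cycle 1 separately from cycles 2-3.
- State that the conclusions apply to patients with an entry score of at least 13.

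The cost is a few lines of SAP text and some programming; no new data are needed. The downside is that the reported gains will look smaller.

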9.9. Pre-global country-specific summary

Each country can process its own data before the final analysis is performed. The pre-global country-specific summary will have descriptive character and no study endpoint hypothesis will be tested, focusing only on frequencies. The pre-global summary will describe population size, demography, treatment details, occurrence of the events, and also will present incidence of adverse events. The full country-specific analysis will be conducted after the global data analysis.

Data to be presented in pre-global country-specific analysis:

- Disposition of patients and analysis sets
- Demography, Disease characteristics data and therapy history (by total and arm)
- Treatment pattern at each visit (by total and arm)
 - Visit details
 - Chemotherapy administration
 - Antiemetic treatment and corticosteroids administration
- Frequency of the endpoint events occurrence (by arm)
- Health economic data (by arm)
- Number of patients with AE occurrence (by arm)

No statistical modelling or testing will be performed. All endpoint events in the pre-global analysis will be presented for the FAS population only, the PP population will be omitted, and imputation of endpoint data will not be performed. Since no imputation will be done, the primary endpoint, proportion of patients with complete response in the overall phase (0-120 hours) over three cycles of chemotherapy, will be analysed only for patient with complete information. They must be treated in all three cycles of treatment with complete CINV information and rescue medication on MAT and PD questionnaires.

Coding of adverse events will be done after all data collection and will not be available for pre-global analysis. Therefore, only the summary of the number of patients with AE will be presented here.

For the pre-global country specific analysis a separate layout of tables will be created, details in Appendix 2.

10. List of Tables, Figures and Listings

The table below presents a preliminary list of tables, figures and listings which will be included in study report. The numbering and structure are proposed according to the ICH guidelines - E3: Structure and Content of Clinical Study Reports.

10.1. Tables and Figures

Output	Numbering	Title	Analysis Set
	14.1	Demographic data	
Table	14.1-1	Disposition of patients and analysis sets	Total Set
Figure	14.1-2	Flow of patients in analysis sets	Total Set
Table	14.1-3	Total number of patients enrolled by centre	Total Set
Table	14.1-4	Reasons for exclusion from analysis sets and protocol deviations	Randomized Set
Table	14.1-5	Study Enrolment by Site	Total Set
Table	14.1-6	Treatment Disposition	Full Analysis Set
Table	14.1-7	Demographic and baseline characteristics	Full Analysis Set
Table	14.1-8	CINV risk parameters at screening	Full Analysis Set
Table	14.1-9	Disease characteristics	Full Analysis Set
Table	14.1-10	Previous therapy history	Full Analysis Set
Table	14.1-11	Visits details	Full Analysis Set
Table	14.1-12	Chemotherapy	Full Analysis Set
Table	14.1-13	Prophylactic antiemetic regimen	Full Analysis Set
	14.2	Efficacy data	
Table	14.2-1	Proportion of patients with complete responses in the overall phase (0-120 hours) over three cycles of chemotherapy	Full Analysis Set, Per Protocol
Figure	14.2-1	Complete response – Logistic Regression	Full Analysis Set, Per Protocol
Table	14.2-2	Patients with Complete response during the acute/delayed/overall phase and daily	Full Analysis Set, Per Protocol
Figure	14.2-2	Complete response during the acute/delayed/overall phase and daily – Logistic Regression	Full Analysis Set, Per Protocol
Table	14.2-3	Number and Percentage of Patients with No Emesis	Full Analysis Set, Per Protocol

Output	Numbering	Title	Analysis Set
Figure	14.2-3	Emetic episodes during the acute/delayed/overall phase and daily – Logistic Regression	Full Analysis Set, Per Protocol
Table	14.2-4	Number of vomiting episodes per patient	Full Analysis Set, Per Protocol
Figure	14.2-4	Vomiting episodes during the acute/delayed/overall phase and daily –Regression	Full Analysis Set, Per Protocol
Table	14.2-5	Number and Percentage of Patients with No Rescue Medication	Full Analysis Set, Per Protocol
Figure	14.2-5	Rescue medication during the acute/delayed/overall phase and daily – Logistic Regression	Full Analysis Set, Per Protocol
Table	14.2-6	Number and percentage of patients with No Significant nausea	Full Analysis Set, Per Protocol
Figure	14.2-6	Significant nausea during the acute/delayed/overall phase and daily – Logistic Regression	Full Analysis Set, Per Protocol
Table	14.2-7	Number and percentage of patients with No Nausea	Full Analysis Set, Per Protocol
Figure	14.2-7	No nausea during the acute/delayed/overall phase and daily – Logistic Regression	Full Analysis Set, Per Protocol
Table	14.2-8	Number and Percentage of patients with Complete protection	Full Analysis Set, Per Protocol
Figure	14.2-8	Complete protection during the acute/delayed/overall phase and daily – Logistic Regression	Full Analysis Set, Per Protocol
Table	14.2-9	Quality of life indicators	Full Analysis Set, Per Protocol
Figure	14.2-9	Quality of life indicators – FLIE	Full Analysis Set, Per Protocol
Table	14.2-10	Chemotherapy delay	Full Analysis Set, Per Protocol
Table	14.2-11	Chemotherapy reduction	Full Analysis Set, Per Protocol
14.3 Safety Data			
Table	14.3-1	Drug Exposure	Safety Set
Table	14.3-2	Overall summary of AE	Safety Set
Table	14.3-3	Treatment emergent AEs by System Organ Class and Preferred Term	Safety Set
14.4 Health Economy Data			
Table	14.4-1	Number of days and daily doses of rescue medication administered for the treatment of CINV	Full Analysis Set

Output	Numbering	Title	Analysis Set
Table	14.4-2	Number of re-hydration bags given for at least grade 2 vomiting (CTCAE grade 5)	Full Analysis Set
Table	14.4-3	Unplanned hospitalisation related to CINV	Full Analysis Set
Table	14.4-4	Outpatient visits and health care consultations due to CINV	Full Analysis Set
Table	14.4-5	Unplanned laboratory tests including those at unplanned hospitalisation due to CINV	Full Analysis Set
Table	14.4-6	Discontinuation of chemotherapy treatment due to CINV	Full Analysis Set
Table	14.4-7	Days of absence from work	Full Analysis Set

10.2. Patient Data Listings

Numbering	Title
16.2.1	Discontinued patients
16.2.1-1	Discontinued subjects
16.2.2	Protocol deviations
16.2.2-1	Protocol deviations
16.2.7	Adverse event listings
16.2.7-1	Adverse events (including pre-treatment)
16.2.7-2	Serious adverse events
16.2.7-3	Adverse events resulting in withdrawal of study drug
16.2.7-4	Deaths

11. Layout of TFLs

Details in Appendix 1.

12. References

- [1] ICH guidelines - E9: Statistical Principles for Clinical Trials, Adopted in EU by CPMP, March 1998, issued as CPMP/ICH/363/96
- [2] ICH guidelines - E3: Structure and Content of Clinical Study Reports, Adopted in EU by CPMP, December 95, issued as CPMP/ICH/137/95
- [3] SAS 9.4; © SAS Institute Inc., Cary, NC, USA; OnLine Doc.
- [5] Lindley, C. M., Hirsch, J. D., O'Neill, C. V., Transau, M. C., Gilbert, C. S., & Osterhaus, J. T. (1992). Quality of life consequences of chemotherapy-induced emesis. *Quality of Life Research*, 1(5), 331-340.
- [6] Cook, N., Reclassification Statistics Retrieved from <http://ncook.bwh.harvard.edu/sas-macros.html>
